### Calculation of multiplicity adjusted one- and two-sided p-values

Multiplicity adjusted p-values will be calculated for each null hypothesis as the smallest significance level at which one can reject that null hypothesis using the testing procedure shown in [Figure 6-4](#) while also taking into account the interim analyses. For this purpose the algorithm described by [Bretz et al. \(2009\)](#) will be applied to the unadjusted one-sided p-values and the resultant p-values (adjusted only for the multiple endpoints and doses) will be adjusted for the interim analyses by scaling them by a factor of 250 (=0.025/0.0001) at the first efficacy interim analysis, 62.5 (=0.025/0.0004) at the second efficacy interim analysis and 0.025/0.0245 ( $\approx 1.02$ ) at the final analysis. Because a weighted Dunnett test will be used for any intersection hypothesis from the full closure that contains at least two of  $H_{11}$ ,  $H_{21}$  or  $H_{31}$ , the algorithm of [Bretz et al. \(2009\)](#) needs to be extended. For this purpose the weights  $w_{11}$ ,  $w_{21}$  and  $w_{31}$  used as part of that algorithm would be defined as the respective Dunnett level divided by the overall significance level at the respective analysis.

For example, for the global null hypothesis instead of  $w_{11}=0.2$ ,  $w_{21}=0.4$  and  $w_{31}=0.4$  as for a Bonferroni test based procedure – for which  $w_{11} + w_{21} + w_{31} \leq 1$  would always hold – instead  $w_{11} + w_{21} + w_{31} > 1$  would hold in this case. For example, using the nominal Dunnett significance levels for 300 mg, 150 mg and 50 mg doses at the final analysis calculated using the mvtnorm package in R as described earlier in [section 6.3.1](#), one obtains  $w_{11} = 0.5500504\% / 2.45\% \approx 0.2245103$ ,  $w_{21} = 1.1001008\% / 2.45\% \approx 0.4490207$  and  $w_{31} = 1.1001008\% / 2.45\% \approx 0.4490207$ .

In case health authorities, journals or the data monitoring committee require two-sided p-values, these will be provided in a manner that firstly ensures that the test decision on the rejection of the primary and key secondary null hypotheses remains unchanged and that secondly uses in principle the same testing procedure for evaluating the potential superiority of placebo over each dose of the test drug.

On this basis, the same test procedure as shown in [Figure 6-3](#) will also be conducted in a one-sided fashion on the 2.5% significance level to test for the superiority of placebo over each canakinumab dose arm. The multiplicity adjusted two-sided p-values for each canakinumab dose arm will then be calculated as the minimum out of

- $2 \times$  the multiplicity adjusted one-sided p-value for the superiority of that canakinumab dose arm over placebo,
- $2 \times$  the corresponding multiplicity adjusted one-sided p-value for the superiority of placebo over that canakinumab dose arm versus
- and 1.

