## **6.3 Statistical hypothesis, model, and method of analysis**

The primary analysis and all analyses of secondary [REDACTED] variables unless otherwise stated will use the Full Analysis Set (FAS), which reflects the intention-to-treat principle.

The familywise type I error rate for this trial will be controlled at the one-sided 2.5% level. One-sided testing at the 2.5% level constitutes an equivalent level of evidence as two-sided testing at the 5% level. Two sided p-values will also be provided.

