Note that no assumption of proportional hazards is necessary to test whether there is a higher probability of MACE in canakinumab than on placebo, because the employed stratified log-rank tests are valid even without proportional hazards. This assumption is only necessary to calculate estimated hazard ratios with confidence intervals for the effect of treatment ([Bland and Altman 2004](#)).

The family-wise error rate will be controlled at the two interim analyses and the final analysis using the closed testing procedure shown in [Figure 6-4](#) based on the graphical method of Bretz et al. ([Bretz, et al 2009](#)); however, in intersection null hypotheses involving the primary null hypotheses for the 300 mg, 150 mg or 50 mg doses these primary null hypotheses will be tested using a weighted version of Dunnett's test ([Dunnett 1955](#)). Specifically this means that for any intersection hypothesis from the full closure that contains at least two of  $H_{11}$ ,  $H_{21}$  and  $H_{31}$ , a weighted Dunnett test amongst the primary null hypotheses is performed with the overall significance level for that test and the weighting chosen according to the weights assigned to these null hypotheses by the update algorithm of the graphical method. The nominal adjusted significance levels based on the weighted Dunnett test are always slightly larger than the corresponding Bonferroni levels would be. For example the `mvtnorm` package in R ([Genz and Bretz 2009](#)) calculates the nominal Dunnett significance levels at the final

analysis for the 300 mg, 150 mg and 50 mg doses versus placebo adjusting for the interim analysis in the test of the global null hypothesis to be 0.5500504%, 1.1001008% and 1.1001008%, respectively, as compared to Bonferroni levels of 0.49%, 0.98% and 0.98%. If other non-primary null hypotheses in such an intersection hypothesis have non-zero weight on the basis of Figure 6-4, the intersection null hypothesis will be rejected if either (a) these other null hypotheses can be rejected at a Bonferroni significance level based on that weight or (b) the primary null hypotheses can be rejected based on the weighted Dunnett test.

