Two efficacy interim analyses, at which the trial could be stopped for demonstrated efficacy, or one or more active arms could be stopped for futility, will be performed respectively after

50% and 75% of the target number of 1,400 patients have experienced a primary endpoint. Futility criteria and the criteria other than purely formal statistical significance required for stopping the trial for demonstrated efficacy will be specified in the Data Monitoring Committee charter. Protocol amendment 8 introduced an additional early futility analysis to be performed at approximately 30% of the target number of 1400 patients have experienced CEC confirmed MACE. The analysis plan of the early futility was discussed in a separate document.

A fixed Bonferroni split of the one sided significance level will be used to account for the two efficacy interim analyses and the final analysis, with a significance level of 0.01% for the first and 0.04% for the second efficacy interim analysis. I.e. the closed testing procedure will be performed with an one-sided significance level of 0.01% at the first efficacy interim analysis, with an one-sided significance level of 0.04% at the second efficacy interim analysis and with an one-sided significance level of 2.45% at the final analysis. In this fashion the familywise type I error rate will be controlled at the overall (one-sided) significance level  $\alpha = 2.5\%$ .

No multiplicity adjustment will be made for the additional early futility analysis, because it will not result in rejecting a null hypothesis for efficacy superiority.

The appropriate nominal weighted Dunnett significance levels will be calculated e.g. using the mvtnorm R package ([Genz and Bretz 2009](#)). For the example of the global null hypothesis this can be done using R code (or corresponding SAS code) similar to the following

```
library(mvtnorm)
alpha <- 0.0245 # level at which Dunnett test is performed
rho <- 0.5 # assumed correlation of test statistics
corr <- (1-rho)*diag(3)+rho # correlation matrix
weight <- c(0.2,0.4,0.4) # weights for hypotheses in Dunnett test
alphaw <- alpha*weight
MVN <- function(alpha1, w, corr, alpha){
  x<-qnorm(1-alpha1*w)
  return(1-pmvnorm(upper=x,corr=corr) - alpha)
}
opt3 <- uniroot(MVN, lower = alpha, upper = 2*alpha, w=weight,
corr=corr, alpha=alpha, tol=1E-12)
critwDun <- qnorm(1-opt3$root*weight)
nominal <- opt3$root*weight
```

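### The adjusted p-values use Dunnett weights fixed at one significance level per analysis, so they match the SAP's own definition only at the decision boundary; decisions are unaffected

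*SAP*

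**What the plan says.** The subsection of SAP 6.3.1 on multiplicity-adjusted p-values begins with a definition. The adjusted p-value is "the smallest significance level at which one can reject that null hypothesis using the testing procedure shown in" Figure 6-4, with the interim analyses taken into account.

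It then gives an algorithm. The graphical procedure's p-value algorithm is applied to the unadjusted one-sided p-values, and the result is multiplied by 250, 62.5 or 0.025/0.0245 according to the analysis. Where an intersection contains two or more primary hypotheses, the weights in that algorithm "would be defined as the respective Dunnett level divided by the overall significance level at the respective analysis". The worked example for the global null at the final analysis gives 0.2245103 for 300 mg and 0.4490207 for each of 150 mg and 50 mg.

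Those weights come from the R code earlier in 6.3.1: "alpha <- 0.0245 # level at which Dunnett test is performed", "rho <- 0.5 # assumed correlation of test statistics" and "weight <- c(0.2,0.4,0.4) # weights for hypotheses in Dunnett test". The nominal levels are stated "in the test of the global null hypothesis to be 0.5500504%, 1.1001008% and 1.1001008%, respectively". Two-sided adjusted p-values are derived by doubling the one-sided values, with a cap at 1.

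**The concern.** Bonferroni weights do not depend on the significance level, so dividing a p-value by its weight gives the smallest rejecting level. Dunnett weights do depend on it. The gain of Dunnett over Bonferroni is small at very low levels and grows as the level rises. Dividing by a weight solved at 2.45% therefore credits a strong result with more gain than exists at its own level, and a weak result with less.

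The definition and the algorithm thus give different numbers for the same data. A programmer working from the definition and one working from the algorithm would report different adjusted p-values. For significant results the algorithm's value is the smaller one, which is the anti-conservative direction. Adjusted p-values are a planned output in Protocol section 9.4.2 as well as in the SAP.

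**Working it through.** **Inputs (SAP 6.3.1).** Weights w = 0.2, 0.4, 0.4 for 300, 150 and 50 mg; correlation 0.5; final-analysis level 0.0245, one-sided.

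**Reproducing the plan's figures.** Solve 1 − P(all Z_i ≤ z(1 − q·w_i)) = 0.0245 for q, with z the standard normal quantile. The nominal levels q·w_i are 0.5498% for 300 mg and 1.0996% for each of the other doses. The SAP states 0.5500504% and 1.1001008%, a relative difference of 0.05%. The exact level at the stated cut-offs is 2.451%, so the figures reproduce. The weights follow: 0.5500504/2.45 = 0.2245 and 1.1001008/2.45 = 0.4490, with a sum of about 1.1226.

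**How the Dunnett gain varies.** The ratio of Dunnett to Bonferroni nominal levels, solved at different overall levels:

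| Overall level | Ratio |
|---|---|
| 0.01% | 1.015 |
| 0.04% | 1.025 |
| 0.1% | 1.035 |
| 1% | 1.084 |
| 2.45% | 1.122 |
| 10% | 1.231 |
| 50% | 1.605 |

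**Planned against defined value.** Take the global-null intersection with 150 mg having the smallest p_i/w_i, so q = p/0.4. The planned value is p/0.4490207. The defined value is 1 − P(all Z_i ≤ z(1 − q·w_i)). Before interim scaling:

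| Unadjusted 150 mg p | Planned | Defined | Planned/defined |
|---|---|---|---|
| 0.0001 | 0.000223 | 0.000245 | 0.91 |
| 0.001 | 0.00223 | 0.00239 | 0.93 |
| 0.002 | 0.00445 | 0.00471 | 0.95 |
| 0.008 | 0.0178 | 0.0181 | 0.99 |
| 0.011 | 0.0245 | 0.0245 | 1.00 |
| 0.05 | 0.111 | 0.101 | 1.10 |
| 0.2 | 0.445 | 0.342 | 1.30 |

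After scaling by 0.025/0.0245, p = 0.002 is reported as 0.00455 instead of 0.00480.

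**Limits.** As p tends to 0 the ratio tends to 1/1.1226 = 0.891, so the understatement cannot exceed about 10.9%. Before the cap at 1 takes hold, the overstatement reaches about 55% for one-sided values (0.645 reported as 1.0) and about 32% for two-sided values (0.756 reported as 1.0).

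**Other intersections.** After H11 is rejected, its weight of 0.2 passes 45% to H21 and 25% to H31. This gives 0.4 + 0.45 × 0.2 = 0.49 and 0.4 + 0.25 × 0.2 = 0.45, with 0.06 left for the 300 mg key secondary hypotheses. For this pair the understatement limit is about 7%. An intersection with a single primary hypothesis uses no Dunnett weight and has no error.

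**Interims.** With weights fixed at 0.01% and 0.04%, the understatement is at most 1.5% and 2.4%, and the overstatement is about 4% and 7%.

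**Decisions.** At the analysis level, both calculations reject an intersection exactly when q is at or below the same critical value. A check on 20,000 random p-value triples for the global null found no disagreement.

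**The case against.** The strongest reply is that nothing inferential depends on this. The boundaries are correct, and the SAP's commitment that "The familywise type I error rate for this trial will be controlled at the one-sided 2.5% level" is untouched. Near the threshold the discrepancy vanishes: at p = 0.01 it is 0.5%. For very small p, 0.00022 against 0.00024 would not change anyone's reading. The largest overstatements fall on plainly non-significant results and are conservative. The SAP introduction also says that a more detailed plan will follow.

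All of that stands, and it limits the importance of the point. It does not remove the mismatch. The SAP gives an explicit formula and a worked example, not an outline, and the formula yields something other than the quantity defined at the head of the same paragraph.

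A reader might infer more: that a dose could be declared significant wrongly, that the familywise error rate is inflated, or that every reported adjusted p-value is off by 10% or 30%. The documents support none of these. The critical values are the same under either calculation. The weights are tied to the level of each analysis, so 2.45% applies only at the final one. The percentages above are for the global-null intersection. The reported value is a maximum over intersections, so those percentages carry through in full only when that intersection is the one that decides.

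**Conclusion.** The point holds as a reporting error. The algorithm departs from the definition "Multiplicity adjusted p-values will be calculated for each null hypothesis as the smallest significance level" at every value except the boundary. In the significant range at the final analysis the reported adjusted p-value is too small by roughly 1% to 9% for unadjusted 150 mg p between 0.008 and 0.0001, with a ceiling near 11%. Above the boundary it is too large, noticeably so only for clearly non-significant results. No rejection decision changes.

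These sizes rest on the SAP's assumed correlation of 0.5 and on the global-null intersection deciding the adjusted p-value. With a correlation of 0.4 or 0.3 used throughout, the ceiling on the understatement falls to about 7% or 5%, and the pattern is the same.

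**What to change.** Replace the fixed-weight rule for every intersection that contains two or more primary hypotheses:

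1. Let w_i be the graph weights on the primary hypotheses in the intersection, W their sum, and q = min(p_i/w_i).
2. Compute the Dunnett part as `(1 - pmvnorm(upper = qnorm(1 - q*w), corr = corr)) / W`, capped at 1.
3. If non-primary hypotheses in the intersection carry non-zero weight, take the minimum of that value and their Bonferroni values p_j/w_j. SAP 6.3.1 allows rejection through either route.
4. For each hypothesis take the maximum over all intersections containing it, then apply the interim scaling factor.

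The division by W is essential. The SAP runs the Dunnett test at the level the graph assigns to the primary hypotheses, which can be below the full level. In the 0.49/0.45 case W is 0.94. Without the division the result would be 6% too small, and the 150 mg boundary would move from 0.01291 to 0.01376, which would change decisions. With it, every boundary stays where it is.

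The cost is one rewritten paragraph and a short function using the R package the SAP already cites, completed before database lock. If the sponsor prefers to keep the present formula, the SAP should at least say that the values are approximations, exact only at the decision threshold.

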A fixed Bonferroni split of the one sided significance level will be used to account for the two efficacy interim analyses and the final analysis, with a significance level of 0.01% for the first and 0.04% for the second efficacy interim analysis. I.e. the closed testing procedure will be performed with a one-sided significance level of 0.01% at the first efficacy interim analysis, with a one-sided significance level of 0.04% at the second efficacy interim analysis and with a one-sided significance level of 2.45% at the final analysis. In this fashion the familywise type I error rate will be controlled at the overall (one-sided) significance level $\alpha = 2.5\%$. This constitutes an equivalent level of evidence as the two-sided 5% level. Multiplicity adjusted p-values will be calculated for each null hypothesis as the smallest significance level at which one can reject that null hypothesis. Both one-sided and two-sided p-values will be reported. To obtain the latter, the same test procedure as shown in [Figure 9-1](#) will also be conducted in a one-sided fashion on the 2.5% significance level to test for the superiority of placebo over each test arm.

The hazard ratios and their associated confidence intervals will be estimated by means of a ([Cox 1972](#)) proportional-hazards model stratified by time since index MI (< 6 months, \geq 6 months) and by trial part using treatment (canakinumab doses and placebo) as a factor in the model using exact method for handling ties. Kaplan-Meier type plots will be presented to summarize the time to first event in the composite endpoint, by presenting the time-dependent

cumulative frequency and percentage of patients who reach the primary composite endpoint by treatment group. Appropriate methods for plotting the overall data from both trial parts together will be pre-specified in the statistical analysis plan. Separate Kaplan-Meier plots by trial part will also be provided.

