To illustrate the link between trial objectives and the close testing procedure, it may be helpful to consider what the procedure might have looked like, if the Dunnett test had not been used. This is shown in Figure 6-3. As discussed in detail below, introducing a Dunnett test required modifications with several additional vertices to ensure consonance (see Figure 6-4).

**Figure 6-3** Possible closed testing procedure if Dunnett test had not been used

All other intersection hypotheses are tested with a weighted Bonferroni test. Protection of the family-wise error rate at level alpha is still guaranteed when the transition weights on the directed edges are chosen as in Figure 6-4 (see comment below the figure) and all the tests on secondary variables are performed at the level resulting from the graphical procedure. The consonance of the test procedure (Brannath and Bretz 2010) has also been ensured as described below.

[figure not shown]
The testing procedure in Figure 6-4 initially splits the entire available significance level (at the final analysis 2.45%) between the three primary null hypotheses relating to the three doses (at the final analysis 20% of 2.45% = 0.49% for the primary null hypothesis of the 300 mg dose, 40% of 2.45% = 0.98% for that of the 150 mg dose and 40% of 2.45% = 0.98% for that of the 50 mg dose). These weights were chosen by balancing the prior expectations about the efficacy dose response relationship versus the potential for a better risk benefit ratio with lower doses. In particular, one aim was to ensure that there would be at least 80% power for the 50 mg dose to become significant assuming a 20% relative risk reduction for all doses. In the process of ensuring this, the weight for the 300 mg dose was reduced more than that of the 150 mg, because a higher dose is only of interest if it demonstrates a better efficacy than lower doses. This means that when the other doses are not effective the 300 mg dose would

only become significant with a relative risk reduction that is at least in the region of 17.5%, while for the 150 mg dose this would already be the case with relative risk reductions below 16%. However, this was considered acceptable in order to ensure the desired operating characteristics for the 150 mg and 50 mg dose.

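### The SAP's two-sided p-value rule cites Figure 6-3, the hypothetical graph without Dunnett, for the placebo-superiority direction; probably a stale cross-reference to Figure 6-4

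*SAP*

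**What the plan says.** The SAP subsection on multiplicity-adjusted p-values, within 6.3.1, works in two steps. For the benefit direction, adjusted one-sided p-values are obtained "using the testing procedure shown in [Figure 6-4](#) while also taking into account the interim analyses", with the graphical algorithm extended so that any intersection holding at least two of the three primary hypotheses is tested by weighted Dunnett. For two-sided p-values it sets two conditions: rejection decisions on the primary and key secondary hypotheses must not change, and the approach "uses in principle the same testing procedure for evaluating the potential superiority of placebo over each dose of the test drug".

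The next sentence turns to the harm direction and calls for "the same test procedure as shown in [Figure 6-3" (the figure number ends the quote), run one-sided at 2.5%. Its stated purpose is "to test for the superiority of placebo over each canakinumab dose arm". The two-sided p-value for a dose is then the smallest of twice the adjusted benefit p, twice the adjusted harm p, and 1.

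Earlier in 6.3.1, Figure 6-3 carries the caption "Possible closed testing procedure if Dunnett test had not been used". It is introduced as an aid to understanding, and the SAP adds that "introducing a Dunnett test required modifications with several additional vertices to ensure consonance", pointing to Figure 6-4 for the result.

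Protocol 9.4.2 covers the same step. It plans to report p-values of both kinds, one-sided and two-sided, and introduces the second kind with "To obtain the latter, the same test procedure as shown in". The graph it names there is Figure 9-1, the one it uses for its confirmatory tests.

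**The concern.** Figure 6-3 is by the SAP's own account not the trial's procedure. It lacks the Dunnett test and has a different structure from Figure 6-4. Naming it for one direction contradicts the sentence just before it in the SAP, and the Protocol.

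This is an operative instruction, not background text. A programmer who follows it literally would feed the two-sided p-value from two different procedures: Dunnett-based levels for benefit and, on the natural reading, Bonferroni levels for harm. If the mismatch were noticed only after unblinding, someone would have to decide then which graph had been meant.

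**Working it through.** **Cross-references side by side**

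| Place | Direction | Graph named | Role of that graph |
|---|---|---|---|
| SAP 6.3.1, adjusted p-values, one-sided step | benefit | Figure 6-4, weighted Dunnett | operative |
| SAP 6.3.1, adjusted p-values, stated aim | harm | in essence the same procedure | operative |
| SAP 6.3.1, adjusted p-values, next sentence | harm | Figure 6-3 | hypothetical, no Dunnett |
| Protocol 9.4.2 | harm | Figure 9-1 | operative; same caption as SAP Figure 6-4 |

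The third row disagrees with the other three. The captions and prose are enough to show this.

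**Inputs for the size (SAP 6.3.1).** Final one-sided level 2.45%; starting weights 0.2/0.4/0.4 for 300/150/50 mg; correlation 0.5 in the SAP's code; final-analysis scaling factor 0.025/0.0245 = 1.0204.

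**Reproducing the plan's Dunnett levels.** Solve for a in P(at least one Z_i > z(1 − a·w_i)) = 0.0245 with equicorrelated normals; the level for dose i is a·w_i. Numerical integration gives 0.5498/1.0996/1.0996%. The SAP states 0.5500504/1.1001008/1.1001008%. They agree to within 0.0006 percentage points, which fits integration error.

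**Literal reading.** Assume Figure 6-3 is a Bonferroni graph with the same starting weights. The global-intersection levels are then 0.2 × 2.45% = 0.49% and 0.4 × 2.45% = 0.98% (twice). The Dunnett levels are larger by 1.0996/0.98 = 1.122, about 12%.

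**Worked example, global intersection only: one-sided harm p = 0.0105 for 150 mg**
- Bonferroni: 0.0105/0.4 = 0.02625; × 1.0204 = 0.02679; doubled, 0.0536.
- Weighted Dunnett, SAP weight 0.4490207: 0.0105/0.4490207 = 0.02338; × 1.0204 = 0.02386; doubled, 0.0477.
- Exact weighted Dunnett probability, scaled: 0.02392; doubled, 0.0478.

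So about 0.054 against 0.048. The verdict at this intersection differs only for a one-sided harm p between 0.98% and 1.10% (150 or 50 mg), or between 0.49% and 0.55% (300 mg).

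**Direction of the effect.** Under the global null with correlation 0.5, the chance of any false harm finding at the final look is 2.19% with the Bonferroni levels and 2.45% with the Dunnett levels.

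**The case against.** The strongest reply is that nobody intended a second procedure. The sentence follows directly from the stated aim of using one procedure in both directions, and the Protocol agrees. On that view this is a wrong figure number and no more. That stands, and it is why the point is framed as a cross-reference error.

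A reader might go further and infer that the plan deliberately holds evidence of harm to a stricter standard than evidence of benefit. The documents do not support this. No text describes a separate harm procedure. The hypotheses are one-sided for benefit, and the two-sided values may not alter those decisions. Safety assessments carry no multiplicity adjustment (SAP 7.1), hazard ratios with confidence intervals are reported whichever graph applies, and the monitoring committee works to its own charter. A reader might also suspect inflated type I error, but the literal reading errs on the conservative side.

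It is also fair to say that the example was chosen inside the narrow window where the verdict changes, and that the 12% belongs to the three-dose intersection alone. An adjusted p-value is the maximum over all intersections containing the hypothesis, and where only one primary hypothesis is present Dunnett gives no gain.

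Finally, the SAP subsection makes two-sided p-values depend on a request from authorities, journals or the monitoring committee. That does not remove the point, because SAP 6.3 and Protocol 9.4.2 provide for them without condition.

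**Conclusion.** The reference to Figure 6-3 is wrong as written: it conflicts with the paragraph before it and with Protocol 9.4.2. It is probably a stale figure number, and correcting it is a minor but worthwhile change.

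Taken literally, it affects only adjusted two-sided p-values driven by the harm direction and makes them somewhat too large. Efficacy rejections rest on Figure 6-4 and do not change, and familywise error control is not threatened.

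The numerical size rests on three assumptions: Figure 6-3, which is not shown, is a Bonferroni graph starting at 20/40/40; the correlation is 0.5; and the final-analysis scaling applies to the harm direction too. It describes the global intersection only. The transition weights are not fully available, so the effect over the full closure cannot be computed.

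**What to change.** In the sentence on the placebo-superiority direction, replace Figure 6-3 with Figure 6-4, so that the weighted Dunnett tests and the interim scaling factors (250, 62.5 and 0.025/0.0245) apply in both directions; a short clause saying so would remove any doubt. A separate reference to Figure 6-5 is not needed, because the SAP describes it as the same procedure drawn with the key secondary detail.

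The cost is one figure number, and at most one clause, changed before unblinding. Nothing in the design, the sample size or the efficacy analysis changes.
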